13.2.1 Definition of an Evaluable Patient

All patients who receive at least 1 dose of ABT-888 are evaluable for assessing overall survival, the primary endpoint of the Phase II part of this study, as well as for evaluating progression free survival and objective response rates.

13.2.2 Design for the Phase II Component:

As mentioned previously OS is the primary endpoint for the assessment of efficacy of the proposed regimen in patients with newly diagnosed DIPG. The following design utilizes the information available from the PBTC contemporary historical control cohort of eligible patients with newly diagnosed non-metastatic DIPG who were treated on the first five PBTC clinical trials (-006 [phase I, imatinib]; -007 [phase I & phase II, gefitinab]; and -014 [phase I & phase II, tipifarnib]). All patients treated on these trials were between 3 and 18 years of age. Each trial is closed to accrual and all surviving patients have been followed for at least two years to estimate the distribution of OS.

Kaplan-Meier estimate of the distribution of overall survival for the 140 patients treated on the first five trials is shown in the following figure and table.

[figure not shown]
Overall Survival Distribution for PBTC BSG Cohort

Tuble 20					
Months since Start of	All Patients				
Therapy	# of Risk	Events	Censored	Prob.	SE
0	140	0	0	100.00	0.00
6	140	19	1	86.35	2.90
12	120	59	1	43.75	4.17
18	60	39	0	15.31	3.00
24	21	7	0	10.21	2.50
30	14	5	1	6.56	2.11
36	8	3	0	4.10	1.64
42	5	1	4	2.05	2.03

Table 20

We will utilize a design approach based on time to event data rather than building the design on a binomial endpoint. Provided a reasonable model could be identified for the outcome data, designs based on time to event endpoints are more informative and make more efficient use of the available data compared to their binomial counterparts both for the purposes of maximizing the overall power of the study and for using the accumulating information for interim monitoring.

The Bayesian approach developed by Thall, Wooten and Tannir⁴⁸ will be used for the purpose of determining the sample size as well as establishing a monitoring rule. This approach was developed for monitoring time-to-event outcomes in the context of a single arm Phase II trial. Failure times are modeled via an Exponential distribution with an Inverse Gamma prior on the mean. The approach utilizes periodic monitoring for early stopping. While the OS distribution of the PBTC historical cohort is not exponential, the simulation results presented in the Thall, Wooten and Tannir⁴⁸ paper illustrate that the proposed approach is robust in cases where the true distribution is Weibull or Lognormal. As shown in the exploratory plots below, Weibull and the Lognormal distributions seem to fit our historical data best.

The TTEDesigner software available from MD Anderson software download page (https://biostatistics.mdanderson.org/SoftwareDownload/) was used for the necessary calculations.

The prior parameters for the experimental treatment mean were estimated based on the PBTC historical cohort described above. As mentioned previously the Inverse Gamma distribution, which is the conjugate prior for to the Exponential distribution, will be used to provide the prior information on the exponential mean. Besides conjugacy, another attractive aspect of the Inverse Gamma distribution is that its parameters have intuitive interpretations. More specifically in this setting the distribution is parameterized by α_s =number of failures in the historical cohort and β_s =total time at risk in the historical cohort. The values of these parameters were calculated from the PBTC historical control cohort described above. Following the recommended approach by Thall, Wooten and Tannir,⁴⁸ for the experimental treatment, we chose a prior that would result in the same median for the experimental treatment as for the historical cohort but with 10 times the variance in the former. This would reflect the *a priori* belief that the two treatments are the same but with much less certainty regarding the experimental treatment. We believe it is reasonable to choose a prior which reflects the belief that the new treatment will lead to a similar outcome as what has been observed to date. If we believe that the experimental treatment is inferior, it would be unethical to conduct this study whereas if we choose a prior that reflects a favorable opinion about the experimental treatment compared to the historical control then such a prior could bias the results in favor of the experimental treatment which is undesirable. The desired effect size is parameterized in terms of the median time to death. The median time to death estimate based on the current PBTC historical cohort is 10.85 months. Following the Brain Malignancy Steering Committee's recommendation we have set the "effect size" at 5.5 months, reflecting a 50% improvement in the primary outcome parameter, which would certainly be a notable "success", if an experimental treatment were to achieve it.

Our historical experience suggests an average accrual rate of 2 patients per month and we propose to monitor the outcome information twice a year (approximately every 6 months) for early stopping in the event of an unsuccessful treatment. This monitoring schedule coincides

with the PBTC DSMB meetings and hence provides a convenient way of providing up to date outcome information to the PBTC DSMB. With respect to early stopping, the design we present below will only stop for futility. This design has a 6.3% probability of stopping early if the median time to death is 16.5 months for the experimental treatment and 63.85% chance of stopping early if the median time to death is 11 months for the experimental treatment. In the latter case, the mean number of patients expected to be enrolled is 45. So on average we would save 15 patients and 7.5 months of accrual in the event that the experimental treatment is ineffective. Otherwise the trial will enroll 60 patients in approximately 2.5 years. Tables providing the input parameters for design specification and the resulting stopping boundaries associated with the design detailed above are given in **Appendix** G.

Barring early stopping, final analysis will be conducted once all patients have been accrued and followed for at least 2 years or to death, whichever is earlier. This duration of follow-up should be adequate to fully characterize the OS distribution even if the hypothesized 16.5 months for median survival is achieved. As mentioned previously, we will provide KM estimates of the OS distribution, in order to describe outcome information based on the proposed regimen. We will also compare the OS distribution from this trial to the OS distribution of the PBTC historical cohort via the log-rank test to test for a difference. In addition, we will perform a Bayesian analysis of the outcome information providing a 95% credibility interval for the median survival estimate. While it is unlikely, since the prior information is based on the PBTC historical data, if the Bayesian and the frequentist analyses lead to conflicting conclusions, additional analyses will be undertaken to explain the discrepancy but ultimately the frequentist inference will be favored over the Bayesian one.

Under the assumption that the survival distributions are exponentially distributed with the above specified medians and that the analysis time is as detailed above, using the unconditional power estimate proposed by Korn and Freidlin⁴⁹ and as implemented in SiZ software package (ver 1.0) the estimated power of this log-rank test based on a 1-sided test and α =0.1 is 87.72%. Since the asymptotic relative efficiency of the log-rank test is 100% in cases where there is no censoring or when there is random but equal censoring in two groups within the family of Weibull distributions⁵⁰ we expect that the power estimate above is relatively accurate. As we have indicated previously, the Weibull distribution fits well to our historical control data and given the fact that the final analysis will be done 2 years after the last patient is enrolled we expect that there will be very little censoring in the data. Additionally even though this estimate relies on a normal approximation, Sun, Peng and Tu⁵¹ have shown that when the sample size is larger than 50 the approximation leads to accurate estimates of power. Additionally Sun, Peng and Tu⁵¹ results indicate that the unconditional power formula based on the exponential assumption performs well if the true distribution of the historical control is Weibull. So assuming that the hazards are proportional between our historical cohort and the cohort to be treated on this study, we expect that the above mentioned power estimate to be reasonably accurate. While the final analysis of the primary objective will be conducted two years after the last patient

begins treatment, we will continue to follow all patients for survival information for at least three years or until death, whichever is shorter. Annually this additional information will be available for reporting. At the time of the final analysis for the primary outcome, we will also provide the KM estimate of the PFS distribution. Tumor response refers to the best response prior to failure (disease progression, death from any cause or second malignancy). Exact confidence interval

estimates will be provided for the sustained objective response (PR + CR) rate. This trial will be monitored by the PBTC DSMB and only the DSMB will have access to summary outcome information until the primary objective of the trial has been achieved. The DSMB meets semi-annually but also meets via teleconferencing if necessary to review and discuss critical events; such as interim analyses. Accrual, demographic and safety data will be reported to the PBTC membership at the PBTC semi-annual meetings.

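### Appendix G's futility boundaries treat a historical mean survival of 13.86 months as the median, so they do not follow from the stated 10.85-month median, 5.5-month effect or tenfold prior variance

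*Combined protocol and SAP*

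**What the plan says.** Section 13.2.2 describes a Bayesian futility rule for overall survival: "Failure times are modeled via an Exponential distribution with an Inverse Gamma prior on the mean". The historical prior has two parameters: alpha, the "number of failures in the historical cohort", and beta, the "total time at risk in the historical cohort". The experimental prior was chosen to give "the same median for the experimental treatment as for the historical cohort but with 10 times the variance in the former".

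On the effect: "The desired effect size is parameterized in terms of the median time to death". The historical value is given as follows: "The median time to death estimate based on the current PBTC historical cohort is 10.85 months". The gain sought is 5.5 months, "reflecting a 50% improvement in the primary outcome parameter". Table 20 shows the "Kaplan-Meier estimate of the distribution of overall survival for the 140 patients treated on the first five trials".

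Appendix G lists the inputs: historical prior (128, 1759.8), experimental prior (3, 27.7134), delta 5.5, cut-off pL 0.00807171 and at most 60 patients. It then gives the minimum total time on test, in days, needed to continue after each number of deaths. Section 13.2.2 states that the design stops early with probability 63.85% at a true median of 11 months (mean enrolment 45) and 6.3% at 16.5 months.

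**The concern.** Failures and time at risk describe an exponential mean, while the effect size is on the median; the two differ by a factor of ln 2. If a mean-scale prior enters a median-scale rule unconverted, the rule compares the new regimen with a historical median the cohort did not have. This is the only outcome-based early-stopping rule in phase II. A reader following 13.2.2 would take the boundaries to judge a 5.5-month gain over 10.85 months, with an experimental prior ten times as variable as the historical one. If neither holds, the table cannot be derived from the text, and pL does not have the meaning the text suggests. The planned Bayesian credibility interval for the median would inherit the error if it reused the same prior and scale.

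**Working it through.** **Scale of the historical prior.** The events in Table 20 sum to 19 + 59 + 39 + 7 + 5 + 3 + 1 = 133, with 7 censored. The numbers at risk at the interval starts sum to 368 and at the ends to 228. Person-months therefore lie between 6 × 228 = 1,368 and 6 × 368 = 2,208, with midpoint 1,788. Appendix G's 1759.8 agrees with that, so it is time at risk in months. Its prior mean, 1759.8/127 = 13.86 months, is a mean survival; the matching exponential median is 13.86 × ln 2 = 9.60 months.

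**Reproducing the table.** Stop when Pr(θ_E > θ_S + 5.5) < 0.00807171. Here θ_S ~ IG(128, 1759.8) and, after d deaths and time on test T, θ_E ~ IG(3 + d, 27.7134 + cT), with 30.4375 days per month. Boundary in days:

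| Reading | 3 events | 10 | 20 | 40 | 59 |
|---|---|---|---|---|---|
| Printed | 216 | 3,745 | 9,659 | 22,595 | 35,472 |
| Priors on the median (c = ln 2) | 216 | 3,745 | 9,658 | 22,597 | 35,481 |
| Priors on the mean, 5.5 on the mean (c = 1) | 150 | 2,596 | 6,695 | 15,663 | 24,593 |
| Priors on the mean, 5.5 on the median (priors and T × ln 2) | 277 | 3,041 | 7,680 | 17,849 | 27,992 |

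Only the median reading fits. It matches all 57 non-zero rows within 0.13% and gives zero for the first two.

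**What the rule then assumes.** The historical median is taken as 13.86 months, with 95% prior interval 11.6 to 16.5, which excludes 10.85. In Table 20, survival is already 43.75% at 12 months and interpolates to 32–35% at 13.86. The internal reference is 13.86 + 5.5 = 19.36 months, and 19.36/10.85 = 1.78. The text implies 10.85 + 5.5 = 16.35.

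This reference sits inside a 0.8% tail criterion, so it is not an observed hurdle. The observed exponential median needed to continue, ln 2 × T/d, is 8.5, 11.0, 12.2 and 12.9 months at 10, 20, 30 and 40 events.

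**Prior conditions.** The variance is β²/[(α−1)²(α−2)].
- Historical: 13.86²/126 = 1.524.
- Experimental: 13.86²/1 = 192.0.
- Ratio: 126, not 10.
- The two priors share a mean (13.86) but not a median (13.8 against 10.4).
- Alpha S is 128, against 133 deaths in Table 20.

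**Size against the rule described.** Take both priors on the median scale, the historical one centred on 10.85 (β_S = 10.85 × 127 = 1,377.95), tenfold variance and the printed pL. Matching prior means gives α_E = 2 + 126/10 = 14.6 and β_E = 10.85 × 13.6 = 147.56. Matching prior medians gives, numerically, 15.633 and 165.15.

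| Events | Printed | Equal means | Printed higher by | Equal medians | Printed higher by |
|---|---|---|---|---|---|
| 10 | 3,745 | 3,577 | 4.7% | 3,354 | 11.7% |
| 20 | 9,659 | 9,006 | 7.2% | 8,807 | 9.7% |
| 30 | 16,010 | 14,622 | 9.5% | 14,438 | 10.9% |
| 40 | 22,595 | 20,359 | 11.0% | 20,185 | 11.9% |
| 59 | 35,472 | 31,477 | 12.7% | 31,315 | 13.3% |

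With equal means, the scale error alone would raise the boundary by about 11% at 20 events (9,993 against 9,006) and 14% at 30 (16,607 against 14,622). The over-wide experimental prior offsets part of this. Under the described priors, the posterior chance of a gain above 5.5 months at the printed boundary is 1.0–1.2, 1.4–1.6, 2.0–2.3 and 2.9–3.1% at 10, 20, 30 and 40 events, not 0.8%.

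**Operating characteristics.** Simulation: exponential survival, 60 patients at 2 per month, looks at months 6, 12, 18 and 24.

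| | Stops, median 11 months | Mean N | Stops, median 16.5 months |
|---|---|---|---|
| Stated in 13.2.2 | 63.85% | 45 | 6.3% |
| Printed table | 62–63% | 45 | 8% |
| Described rule, printed pL | 47–51% | 47–49 | 4–5% |

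At the printed pL the last two rules disagree in 11–16% of trials at 11 months and 3–4% at 16.5 months, always with the printed table stopping and the described rule continuing.

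**The case against.** The arithmetic is not in dispute; the consequence is. A cut-off tuned for one pair of priors has no standing under another, so the fixed-pL comparison exaggerates the gap. That largely stands: with pL re-chosen at 0.012 (equal means), disagreement with the printed table falls to about 5% of trials at 11 months and 2% at 16.5 months.

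Section 13.2.2 promises operating characteristics, not a posterior meaning for pL, and the printed table comes close to them. It also says survival is not exponential. Under a Weibull (shape 1.61) or lognormal (sigma 0.59) fitted to Table 20, the printed table stops 0.6% or 0.02% of trials at 16.5 months and 62% or 44% at 11 months. Its strictness therefore almost never stops an effective regimen, and a recalibrated rule would stop fewer ineffective ones (56–57% or 36–37%). These points also stand.

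The comparator also departs from the text: a beta of about 1,378 is no longer time at risk. True, but under an exponential model the time-at-risk definition and the 10.85-month median cannot both hold, since 1759.8 converted by ln 2 gives 9.60.

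Finally, the look schedule is assumed. Adding a month-30 look moves the printed table's stopping at 11 months to 69–78%. None of this makes the appendix follow from the text.

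**Conclusion.** The concern holds. The printed boundaries rest on a historical median of 13.86 months, a reference of about 19.4 months and a variance ratio of 126. Section 13.2.2 states 10.85 months, a 5.5-month gain (16.35) and a ratio of 10. At the printed pL the table is about 5 to 13% stricter than the rule described, and part of that gap disappears once pL is re-chosen.

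The fault lies in the specification and meaning of the rule; no gross failure of its performance is shown. The stopping rates quoted assume looks only during accrual, because 13.2.2 counts the benefit of early stopping in patients and months of accrual saved; they assume exponential survival except where another model is named. No patient-level harm during accrual is shown, and the final log-rank comparison and its power are unaffected. The 128-against-133 discrepancy is minor: using 133 moves the equal-means boundaries by 0.3–1.0%. This should be fixed.

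**What to change.** **Full correction.** Put both priors on the median scale and centre the historical one on 10.85 months (beta S about 1,378 at alpha S = 128, after reconciling 128 with the 133 deaths). Choose an experimental prior that meets the tenfold-variance sentence, saying whether means or medians are matched (alpha E about 14.6 or 15.6), or correct that sentence. Re-choose pL by simulation, including the Weibull and lognormal models that 13.2.2 says fit best. Replace the Appendix G table and restate the two stopping probabilities and mean enrolment. Multiplying 1759.8 by ln 2 is not enough, because it centres the historical median on 9.60.

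The cost is one software rerun, a new table and three figures. Under exponential survival with looks to month 24, pL of 0.012 (equal means) or 0.014 (equal medians) gives about 60% stopping at 11 months, 8–9% at 16.5 months and mean enrolment 44–45. Holding false stopping near 6% gives about 54% and 46–47. Under the Weibull or lognormal fits the loss of futility stopping at 11 months is about 5 to 8 points.

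**Minimum alternative.** Keep the printed table for its operating characteristics. Add two or three sentences to 13.2.2 saying that it uses a historical median of 13.86 months and a reference of about 19.4, that the variance ratio is 126, and that pL is a tuning constant, not the posterior probability of a 5.5-month gain over 10.85.

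### The stated 87.72% power leaves out the futility rule: under the plan's exponential assumption the whole design has about 82-84%, and the printed boundary stops about 8% of effective trials, not 6.3%

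*Combined protocol and SAP*

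**What the plan says.** Section 13.2.2 compares 60 new patients with 140 historical controls. During the trial "we propose to monitor the outcome information twice a year (approximately every 6 months) for early stopping in the event of an unsuccessful treatment", using the futility-only boundary tabulated in Appendix G. Two stopping probabilities are given: "This design has a 6.3% probability of stopping early if the median time to death is 16.5 months for the experimental treatment", and a "63.85% chance of stopping early if the median time to death is 11 months for the experimental treatment", the latter with a mean enrolment of 45.

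The final test is conditional on surviving those looks: "Barring early stopping, final analysis will be conducted once all patients have been accrued and followed for at least 2 years". For that test, using an unconditional historical-control formula with exponential survival, "the estimated power of this log-rank test based on a 1-sided test and α =0.1 is 87.72" per cent.

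The same section concedes that "the OS distribution of the PBTC historical cohort is not exponential" and reports the Weibull and lognormal as the best fits. On meetings it says that "The DSMB meets semi-annually but also meets via teleconferencing if necessary to review and discuss critical events". It does not say whether the boundary stays in force once accrual has ended.

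**The concern.** A trial of an effective regimen succeeds only if it passes every futility look and then rejects at the end. The stated power covers the second step alone. The 6.3% covers the first. No figure is given for both together, so a reader is likely to take 87.72% as the chance that this design detects a 16.5-month median.

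Two further things are at stake. If 6.3% does not follow from the printed boundary, the documented cost of the rule is wrong. And if the data monitoring board is not told when the boundary lapses, it could apply it at meetings for which the quoted figures do not hold.

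**Working it through.** **Inputs.** Section 13.2.2: 140 historical patients with at least two years of follow-up, historical median 10.85 months (11 in the stopping calculation), effect 5.5 months, 60 patients, 2 per month, six-monthly looks, one-sided alpha 0.10, final analysis 24 months after the last patient. Appendix G: the boundary in days. Assumed: no dropout, even arrivals, 30.4375 days per month.

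**Step 1: reproduce 87.72%.** Power = Φ( ln(ratio of medians) / √(1/d0 + 1/d1) − 1.2816 ).

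- With λ = ln 2/16.5 = 0.04201, 30 months of accrual and 24 of follow-up, d1 = 60 × [1 − (e^(−24λ) − e^(−54λ))/(30λ)] ≈ 47.6 deaths.
- d0 = 128 (Appendix G), 16.5 v 11: 0.4055/0.1698 − 1.2816 = 1.107, power 86.6%.
- d0 = 140, 16.5 v 10.85: 0.4192/0.1678 − 1.2816 = 1.217, power 88.8%.

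The stated 87.72% lies in this range. The formula has no stopping term, so it is the power without futility looks.

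**Step 2: what the plan's own figures allow.** If every wrongly stopped trial would have been positive, joint power is 87.72 − 6.3 = 81.4%. If none would have been, it is 87.7%.

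**Step 3: apply the printed boundary.** 40,000 simulated trials per case, exponential survival, looks at months 6, 12, 18 and 24:

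| Medians (months) | Power, no rule | Stopped early | Of those, would have been positive | Joint power |
|---|---|---|---|---|
| 16.5 v 11 | 87.0% | 8.3% | 59% | 82.2% |
| 16.35 v 10.85 | 87.6% | 8.8% | 61% | 82.3% |
| 16.5 v 10.85 | 88.6% | 8.3% | 62% | 83.5% |

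First row: 8.3 × 0.59 = 4.9 points lost, and 87.0 − 4.9 ≈ 82.1, agreeing up to rounding. Against 87.72%, the shortfalls are 5.5, 5.4 and 4.2 points. With looks starting at month 12, joint power is 82.6%, 82.7% and 83.9%. At 11 v 11, one-sided error falls from 9.5% to 7.2%.

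Over the accrual range in section 13.3: at 1.5 per month, joint power is 80.3-81.6% with 11.8% false stopping; at 2.5 per month, 82.1-83.5% with 6.8%.

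**Step 4: check the 6.3%.** At 2 per month, looks during accrual stop 62-63% of trials at an 11-month median with 45-46 patients enrolled, close to the stated 63.85% and 45. The same settings stop 7.8% (first look at month 12) to 8.3% (month 6) at 16.5 months.

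- None of 84 combinations of accrual rate, arrival pattern and look schedule gave 6.3%, 63.85% and 45 together. The nearest to 6.3% at 2 per month was a first look at month 18, giving 6.6%, 61.1% and 48.7 patients.
- With 2,000 software runs (assumed; 63.85% is then 1,277/2,000), the gap is 2.5-3.2 standard errors.
- The table is not garbled: rows 3-59 follow from the Appendix G inputs to within 8 days if the prior is read as one on the median.

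**Step 5: Weibull.** Section 13.2.2 says of the effect that "The desired effect size is parameterized in terms of the median time to death", while its power argument assumes proportional hazards. Under a Weibull these differ, so both are shown. The shape is assumed at 1.57, range 1.4-1.8; Table 20 gives about 1.61.

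- Hazard ratio 0.667: joint power 84.3-85.0%.
- Medians 16.35 v 10.85 kept: joint power 97.1-99.7%, false stopping 0.3-1.7%.

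**Step 6: looks after accrual.** Adding one look at month 30 raises null stopping to about 79%, so the stated 63.85% fits looks during accrual only. With looks to month 48, the exponential stops 15-16% at 16.5 months and joint power is 79%. Under the Weibull at shape 1.57, joint power is 63-65% with medians kept (47-75% over the shape range) and 8-9% at hazard ratio 0.667 (1-30%). The reason is visible in Appendix G: at 59 deaths it requires 35,472/30.4375/59 = 19.75 months on test per death, whereas mean survival at shape 1.57 is 18.55 months (medians kept) or 15.93 months (hazard ratio 0.667).

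**The case against.** The strongest reply is that nothing stated is false. The plan attaches 87.72% to the log-rank test, names a fixed-sample method, and discloses the stopping probability and the conditional final analysis just before it. A careful reader can bound joint power, and 82-84% lies inside that bound. This stands: the fault is an omitted figure, not a miscalculated one.

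Second, the exponential is a model the plan itself regards as a poor fit. That also stands. With the stated medians kept under a Weibull, 87.72% is conservative. But the plan's own power argument rests on proportional hazards, and the Weibull case on that basis (about 85%) is also below 87.72%.

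Third, the software's arrival model, look trigger and run count are not documented, so the cause of 8% versus 6.3% cannot be identified. The gap is about 2 points and secondary. The main point does not need it: shrinking the boundary until it stops about 6.3% still gives joint power of about 83.5%.

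Fourth, section 13.2 counts eligible Phase I patients treated at the recommended dose towards the 60, and the simulation starts everyone from zero. Assuming 3-6 such patients who entered 2.5-9 months earlier, false stopping is 8.2-9.7% and null stopping 68-72%. So 82-84% is not exact for the trial as it would run, but the feature moves stopping further from 6.3%.

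Finally, stopping is described in terms of patients and accrual time saved, so looks in follow-up may never have been intended. That is plausible. However, the text does not say so, and the boundary is tabulated up to 59 of 60 deaths.

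**Conclusion.** The concern holds. The only power figure in the plan omits the plan's own futility rule, and the 6.3% does not agree with the printed boundary at settings that nearly return the other two stated figures. The sizes rest on exponential survival, 2 patients per month, looks during accrual only and no dropout.

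This does not show that the trial is underpowered, and the type I error is not inflated. The larger practical risk is the unstated end of monitoring, because the rule's behaviour changes sharply if the boundary is applied during follow-up.

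**What to change.** In section 13.2.2:

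1. Label 87.72% as the power of the final test excluding early stopping.
2. Report simulated joint power as the power of the design: about 82-84% under the exponential, with the Weibull values beside it for both readings of the effect (hazard ratio 0.667, and medians kept).
3. Re-run the stopping probabilities and print the accrual, look and prior settings used, so that the text and Appendix G agree. The re-run will show whether the 6.3% or the boundary needs correcting.
4. State the look schedule to which the operating characteristics apply, and whether the boundary is used after accrual ends, noting that the quoted figures match looks during accrual only.

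The cost is one simulation run and a few sentences. Sample size and final test stay as they are; the stated exponential power becomes about 4-6 points less favourable.

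### The 87.72% power in section 13.2.2 holds for exponential survival; it does not carry over to the Weibull shape of the historical cohort at the plan's own medians, where power is about 99%

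*Combined protocol and SAP*

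**What the plan says.** All of this is in section 13.2.2.

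- **Effect scale.** The target is set on median survival. "The median time to death estimate based on the current PBTC historical cohort is 10.85 months", and the effect size is 5.5 months, "reflecting a 50% improvement in the primary outcome parameter". The early-stopping properties use rounded medians: "63.85% chance of stopping early if the median time to death is 11 months", with 16.5 months as the target.
- **Stated power.** "Under the assumption that the survival distributions are exponentially distributed with the above specified medians", "the estimated power of this log-rank test based on a 1-sided test and α =0.1 is 87.72"%.
- **Shape of the historical data.** The plan accepts that the cohort's survival is not exponential and reports that "Weibull and the Lognormal distributions seem to fit our historical data best".
- **Carry-over.** It cites the efficiency of the log-rank test within the Weibull family, the good Weibull fit and the long follow-up ("we expect that there will be very little censoring in the data"). Assuming proportional hazards, it concludes that "we expect that the above mentioned power estimate to be reasonably accurate".

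Neither the fitted Weibull shape nor a target hazard ratio appears in the readable text.

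**The concern.** Full efficiency of the log-rank test describes how well the test performs at a given hazard ratio. It does not say which hazard ratio a pair of medians implies, and that depends on the shape. For exponential survival the hazard ratio equals the ratio of medians. For a Weibull with shape above 1, the same two medians are further apart in hazard. A power figure worked out at the exponential hazard ratio therefore cannot also describe Weibull data with the same medians.

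The final log-rank comparison is the inference the plan says it will favour if it conflicts with the Bayesian analysis. Its power at the target is a stated design property. A reader of 13.2.2 would take it that the trial has about 88% power for a 5.5-month gain under realistic survival. The reader would not learn that, under the shape the plan endorses, it has that power for a gain roughly half as large.

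**Working it through.** **Inputs.** 60 patients over 30 months and 24 months' minimum follow-up (13.2.2); 140 historical patients. Historical deaths: 128 in Appendix G, while the event column of Table 20 sums to 19+59+39+7+5+3+1 = 133. I use 133 and show 128-140 as a range. Medians are 10.85 or 11 months against 16.5 (10.85 + 5.5 = 16.35 changes little). Assumptions not in the plan: uniform accrual and no dropout.

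**Formulas.**
- Hazard ratio under proportional-hazards Weibull: HR = (m0/m1)^k.
- Expected deaths in the new cohort: d1 = 60 × the average over t from 24 to 54 months of [1 − exp(−ln 2 · (t/m1)^k)].
- Power = Φ(|ln HR| / √(1/d0 + 1/d1) − 1.2816), for one-sided alpha 0.10.

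**Step 1: reproduce the plan (k = 1).** For 11 v 16.5 months: HR = 0.667, |ln HR| = 0.4055, d1 = 47.6, SE = √(1/133 + 1/47.6) = 0.169, z = 2.40, power = Φ(1.118) = 86.8%. For 10.85 v 16.5 months: HR = 0.658, power 88.5%. With 128 to 140 historical deaths the range is 86.6% to 88.8%, which brackets 87.72%. Simulated log-rank tests (4,000 runs each) gave 86.4% and 89.0%.

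**Step 2: shape of the historical curve.** An exponential with median 10.85 months predicts 68%, 32% and 10% alive at 6, 18 and 36 months. Table 20 shows 86.35%, 15.31% and 4.10%. Grouped-data maximum likelihood on Table 20 gives k = 1.61. Log-log regression gives 1.70 (rows to 36 months) and 2.05 (rows to 24 months). The fit is imperfect: the local slope ln[ln S(b)/ln S(a)]/ln(b/a) is about 2.5 between 6 and 12 months and about 1.2 between 12 and 36. I therefore take 1.2 to 2.0 as the range.

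**Step 3: power at the plan's medians under that shape** (d0 = 133, alpha 0.10; each range runs from 11 v 16.5 to 10.85 v 16.5 months).

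| k | HR | d1 | Power |
|---|---|---|---|
| 1.0 | 0.667-0.658 | 47.6 | 86.8-88.5% |
| 1.2 | 0.615-0.605 | 50.4 | 95.2-96.1% |
| 1.4 | 0.567-0.556 | 52.7 | 98.6-99.0% |
| 1.6 | 0.523-0.511 | 54.5 | 99.7-99.8% |
| 1.9 | 0.463-0.451 | 56.5 | above 99.9% |

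Worked line for k = 1.6, 11 v 16.5: 1.6 × 0.4055 = 0.649; SE = √(1/133 + 1/54.5) = 0.161; z = 4.03; power = Φ(2.75) = 99.7%. Simulation also gave 99.7%. If a futility stop under Appendix G counts as failure, simulated power at k = 1.6 is about 98%. That figure is rough, because the same simulation stopped about 11.5% of trials under exponential survival at 16.5 months, against the plan's 6.3%.

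**Step 4: what would make 87.72% carry over.** Hold HR at 0.667 and let the median follow: m1 = 11 × 1.5^(1/k). This gives 14.7, 14.2 and 13.5 months for k = 1.4, 1.6 and 2.0, with power 89.3%, 89.9% and 90.5%.

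**Step 5: median at which power is about 88%** (from 10.85 months, d0 = 133): 15.2 months at k = 1.2, 14.4 at 1.4, 13.8 at 1.6 and 13.3 at 1.9. For k of 1.4 to 1.9 that is a gain of about 2.4 to 3.5 months, not 5.5.

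**The case against.** The best defence is that the carry-over sentence is conditioned on proportional hazards, and on the hazard-ratio scale it is about right: at HR 0.667 Weibull power is close to 90%. That arithmetic stands (step 4). It does not rescue the sentence, because 13.2.2 defines the effect by medians and names 16.5 months. Holding the hazard ratio means giving up that target.

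Three further points stand:

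- **The error is conservative.** Power at the target is at least what is stated, and no sample size or decision rule is harmed by it.
- **The shape is my estimate** from eight grouped rows of Table 20, and the Weibull fit is imperfect. Even at k = 1.2 the stated figure is about 8 points low.
- **The remark about little censoring is not a useful target.** About 21% of the new cohort would be censored under the exponential alternative (47.6 of 60 die), but only about 9% at k = 1.6 (54.5 of 60). Using the exponential percentage against a statement about Weibull data would mix models.

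A reader might also infer that one-sided alpha 0.10 is needlessly lax. The documents do not support that. There is room for a stricter alpha only if both the Weibull shape and the 16.5-month median hold. Under the plan's own exponential assumption, one-sided 0.05 gives 77-80% power and 0.025 gives about 67-70%. At k = 1.2, 0.025 gives about 84-86%. The choice of alpha is a design judgement.

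**Conclusion.** The concern holds for the carry-over statement only. At the plan's medians, with proportional hazards and k of about 1.6, power at one-sided 0.10 is about 99.7% rather than 87.72%, so the stated figure is about 12 points low. Over k = 1.2 to 2.0 the gap is roughly 8 to 12 points. This rests on a shape fitted to Table 20, uniform accrual, no dropout, and no deduction for futility stops.

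A reader might conclude that 87.72% is itself a miscalculation. It is not: it is given for exponential survival and reproduces there. Nor do the documents treat a significant test as proof of a 5.5-month gain, since Kaplan-Meier estimates and a credibility interval for the median are planned alongside it. What is missing is a clear statement of the scale and shape to which the power refers.

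**What to change.** In section 13.2.2, replace the sentences that extend 87.72% to Weibull data with a short statement that:

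1. gives the fitted Weibull shape for the historical cohort and the target hazard ratio it implies at 16.5 months;
2. reports power at the 16.5-month target under that shape, beside 87.72% labelled as the exponential case;
3. states the median at which power is about 88% under that shape (about 13.3 to 14.4 months for k from 1.9 down to 1.4, from 10.85 months).

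The cost is a wording change, plus a shape parameter that should be available from the fits behind the plan's exploratory plots. Sample size, alpha, stopping boundaries and follow-up stay as they are.
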